### 3.1.2. Change in laboratory assessments

Laboratory assessments include all hematology and chemistry parameters as collected in the study (excluding hemoglobin, reticulocytes, lactate dehydrogenase, and unconjugated bilirubin – these parameters belong to the secondary endpoints list. See Section 3.2.2).

For eGFR (estimated Glomerular Filtration Rate), data will be summarized as collected in mL/min/1.73m^2 unit. Data for participants whose baseline result (reported in mL/min) comes from the parent study will be excluded from the analyses.

Change will be described using change from baseline. Rules for defining baseline are described in Appendix 1.2.

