**Table 5. Objectives, Endpoints and Estimands**

Objectives	Endpoints	Estimands
Primary:	Primary:	Primary:
To evaluate the long-term safety of osivelotor in participants with SCD.	
 
Incidence of TEAEs, changes in laboratory assessments, and changes in vital signs.
 
	The safety estimand for the primary endpoints will consider all safety data collected. Specifically, all data collected on or after obtaining informed consent will be included in the analysis.
Secondary:	Secondary:	Secondary:
To evaluate frequency of SCD-related complications.  To evaluate the effects of long-term use of osivelotor on hemolytic anemia.	
 
Annualized rate of VOC.
 
Incidence of SCD-related SAEs.
 
Change from baseline in hematological laboratory parameters, including hemoglobin, reticulocytes, lactate dehydrogenase, and unconjugated bilirubin.
 
	Not Applicable
Exploratory:	Exploratory:	Exploratory:

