### Adult Participants

	AKI (including DIKI) Any one of the below	DICI
Scys & Screat	Simultaneous, confirmed serum cystatin C (Scys) increase and confirmed Screat increase	Confirmed Screat increase without confirmed increase in reflex Scys AND
eGFR	Decrease in Screat-based eGFR and combined Screat-Scys-based eGFR (when available)	Confirmed Screat-based eGFR decrease without confirmed combined Screat-Scys-based eGFR decrease.
Albuminuria or proteinuria	Confirmed albuminuria increase (see Section 11.5 for Grades A1 to A3 quantitation)	
Urine volume	Urine volume <0.5 mL/kg/h for 6 consecutive hours	

Regardless of the presence or absence of increase in Screat, DIKI and other causes of AKI may be suspected if either (i) new-onset or worsening albuminuria or proteinuria are detected or (ii) urine volume (if measured) is <0.5 mL/kg/h for 6 consecutive hours.

All confirmed cases of clinically relevant decrease in kidney function should be considered potential cases of DIKI if no other reason for the kidney function abnormalities has been found.

See [Appendix 2: Liver Safety: Suggested Actions and Follow-Up Assessments](#) for instructions for laboratory testing to monitor kidney function and reporting laboratory test abnormalities.

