#### 9.3.3. Clinical Laboratory Tests

Blood and urine for clinical laboratory tests (Table 9) will be collected as outlined in the SoA (Section 2.1). A certified central laboratory will be utilized to process and provide results for the clinical laboratory tests. The Baseline laboratory test results for clinical assessment for a particular test will be defined as the last measurement prior to the first dose of study drug.

Prior to initiation of treatment, if a participant has an out-of-range value for a clinical laboratory parameter that the Investigator believes is not clinically significant or that the Investigator does not believe is correct (eg, laboratory or specimen processing error), but the Investigator wants to confirm with a repeat laboratory test, a single repeat is allowed to confirm the initial result.

All out of-range values will be assessed by the Investigator as clinically significant or not clinically significant. For any laboratory test value outside the reference range that the Investigator considers clinically significant during the on-study period (ie, following dose administration), the Investigator will repeat the test to verify the out-of-range value and

clinical significance. Clinically significant laboratory abnormalities will be recorded in the AE eCRF (see Section 9.4.7.2).

For pediatric participants,

- Blood draws will be minimized (see Section 9.3.3.1).
- Encourage pain management techniques, for example, cold spray, lidocaine cream, Buzzy Bee, massage, guided imagery, heat/cold packs.
- Reduce fear by providing comfort items/swaddling, parental presence, medical play therapy so children know what to expect, distraction (toys, videos, music), and/or provide a reward system after necessary painful procedures.

See Section 11.4 for suggested actions and follow-up assessments regarding liver safety in the event of potential DILI.

See Section 11.5 for guidelines on laboratory testing to monitor kidney function and reporting laboratory test abnormalities.

Additional safety laboratory tests may be conducted as needed by the Investigator to evaluate participant safety.

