**Table 9. Clinical Safety and Other Laboratory Tests**

Hematology	Chemistry	Urinalysis	Other
Hematocrit	ALT	Albumin	EPO
Hb	Albumin	Bilirubin	FSH (postmenopausal females only)
RBC count	Alkaline phosphatase	Blood	Pregnancy –serum and urine (females who are post menarche and of child-bearing potential) b
Mean corpuscular volume	AST	Creatinine	
Mean corpuscular Hb	Bicarbonate	Glucose	
Mean corpuscular Hb concentration	Blood urea nitrogen	Ketones	
Reticulocyte count (absolute and %)	Calcium	Leukocytes	
Platelet count (estimate not acceptable)	Chloride	Microscopic analysis of sediment if clinically indicated	RBC deformability
White blood cell count including differential count (percent and absolute):	Creatine phosphokinase	Nitrite	Flow Adhesion
Neutrophils	Creatinine	pH	RBC Mitochondrial Content
Lymphocytes	Fasting glucose	Protein	Peripheral Smear
Monocytes	Globulin	Specific gravity	Serum cystatin C
Basophils	Lactate dehydrogenase	Urobilinogen	Haptoglobin
Eosinophils	Magnesium		Hemopexin
PT	Phosphorous		Soluble C3
aPTT	Potassium		
INR	Sodium		
	Total bilirubin (direct and indirect)		Serology Panel (if clinically indicated):
	Total protein		HIV antibody
	Uric acid		Hepatitis A virus IgM antibody
	eGFR a		Hepatitis B virus surface antigen
			Hepatitis C virus antibody

Abbreviations: ALT, alanine aminotransferase; aPTT, activated partial thromboplastin time; AST, aspartate aminotransferase; CKD-EPI, chronic kidney disease epidemiology; eGFR, estimated glomerular filtration rate; EPO, erythropoietin; FSH, follicle stimulating hormone; Hb, hemoglobin; HIV, human immunodeficiency virus; IgM, immunoglobulin M; INR, International Normalized Ratio; PT, prothrombin time; RBC, red blood cells.

a Using CKD-EPI equations (for adults 18 years and above), Cockcroft-Gault formula (for adolescents 12 to <18 years), Modified Schwartz Equation (for children 2 to <12 years), or Schwartz equation (for infants 6 months to <2 years), see Section 11.5.2.

b Tests will be conducted at the clinic.

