#### 10.3.2. Primary Endpoint(s)/Estimand(s) Analysis

Primary Endpoints	Statistical Analysis Method

 
Incidence of TEAEs
 
Changes in laboratory assessments
 
Changes in vital signs
 
	Descriptive statistics of TEAEs, safety laboratory data and vital signs observed values and change from baseline will be provided. Safety data will be presented in tabular or graphical format and summarized descriptively, where appropriate.

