## 6. ANALYSES AND SUMMARIES

### 6.1 Primary Endpoint(s)

The safety estimand for the primary endpoints will consider all safety data collected. Specifically, all data collected on or after obtaining informed consent will be included in the analysis.

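### SAP 3.1.2 limits the primary laboratory endpoint to hematology and chemistry, so the scheduled urinalysis has no planned summary and the omission is not declared

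*SAP*

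**What the plan says.** Protocol Table 5 gives the primary endpoint as "Incidence of TEAEs, changes in laboratory assessments, and changes in vital signs", with no restriction to particular panels. Protocol 10.3.2 sets the analysis: "Descriptive statistics of TEAEs, safety laboratory data and vital signs observed values and change from baseline will be provided". Protocol 9.3.3 begins with "Blood and urine for clinical laboratory tests" and points to Table 9, titled "Clinical Safety and Other Laboratory Tests", whose columns are hematology, chemistry, urinalysis and other. The urinalysis column includes protein, albumin, blood, creatinine and glucose.

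SAP 2.2.3 states that only participants from C5351004 Part A entered this study. For them, Protocol Table 1 (delayed start) and Table 2 (no delay) both schedule urinalysis at Baseline, Week 12, Week 24, every 12 weeks, and EOS/ET.

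SAP 3.1.2 then narrows the endpoint: "Laboratory assessments include all hematology and chemistry parameters as collected in the study", minus hemoglobin, reticulocytes, lactate dehydrogenase and unconjugated bilirubin, which are secondary. SAP 6.1.2 plans descriptive statistics for each parameter so defined. In SAP Appendix 1, the laboratory windows in Tables 3 and 5 are titled as hematology and chemistry.

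**The concern.** A panel that the protocol schedules as safety laboratory work falls out of the analysis of a primary endpoint, and nothing in the SAP says this was intended.

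What is at stake is mainly the renal signal. Protocol 8.2.1, under the adult criteria, says kidney injury may be suspected whether or not creatinine has risen if "new-onset or worsening albuminuria or proteinuria are detected", so creatinine summaries do not cover the same ground. The eGFR summary is also incomplete, because SAP 3.1.2 excludes participants whose baseline came from the parent study in mL/min. Urinalysis is the only urine safety panel that the schedules call for routinely; the albumin-to-creatinine ratio has no row of its own.

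**Working it through.** There is no arithmetic to reproduce beyond simple counts. The check sets the texts side by side.

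1. **Panels.** Protocol Table 9 names three standard panels: hematology, chemistry and urinalysis. SAP 3.1.2 covers 2 of the 3.
2. **Items.** The urinalysis column has 13 entries: albumin, bilirubin, blood, creatinine, glucose, ketones, leukocytes, sediment microscopy, nitrite, pH, protein, specific gravity and urobilinogen. Microscopy is done only if clinically indicated, so 13 − 1 = 12 are routine.
3. **Planned outputs.** SAP 4 assigns labs to the safety analysis set without naming panels, so 3.1.2 is the controlling definition. SAP 6.1.2, the other summaries in 6.5 and the listings (adverse events, deaths, VOC, PK concentrations, potential Hy's law cases, weight) contain no urine result. Planned summaries of measured urine values: 0.
4. **Declaration.** SAP 2.1 lists four modifications: VOC data after intercurrent events, hematology data after intercurrent events, the PK analysis set, and the change from SCD-related SAEs to SCD-related AEs. None concerns urinalysis.
5. **Albumin-to-creatinine ratio.** It is an exploratory endpoint in Protocol Table 5 and in the SAP 2.2 table. SAP 3.3 and 6.3 have six subsections each, on flow adhesion, sickling, RBC deformability, erythropoietin, patient-reported outcomes and PK. None covers the ratio. SAP 2.2 says the presentation of exploratory endpoints may be modified and is described in 6.3, but 6.3 is silent on it.
6. **What still gets through.** Protocol 9.3.3 and 9.4.7.2 send clinically significant laboratory abnormalities to the AE page. Protocol 11.5.4 has a grading row for proteinuria, and SAP 6.1.1 tabulates TEAEs by SOC, preferred term and maximum severity. Proteinuria reported as a TEAE is therefore counted.
7. **What does not get through.** Any urine change not judged clinically significant is lost. The adult Grade 1 entry in Protocol 11.5.4 includes proteinuria of 1+. If protein is reported on that scale, a move from negative to 1+ that the investigator does not consider clinically significant would appear in no output, however many participants showed it.

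**The case against.** The strongest opposing case has five parts.

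- **Proteinuria is not invisible.** A reader might infer that proteinuria and albuminuria are never analysed. The documents do not support that: step 6 shows a route into the TEAE tables, and TEAE incidence is itself a primary endpoint. This stands. What is missing is any summary of measured values. The AE route does not replace one, because it depends on individual judgement and the protocol lists laboratory changes as a separate primary endpoint.
- **The estimand sentence may not be contradicted.** SAP 6.1 says "all data collected on or after obtaining informed consent will be included in the analysis", and a reader might infer that omitting urinalysis directly contradicts it. In Protocol 10.1.1 the same statement sits under intercurrent events, so it can be read as a rule that no data are discarded because of an event. That reading is fair, and the point does not rest on a contradiction.
- **The extent can be overstated.** Not all 13 items are lost for every participant at every visit, since one is conditional. The documents give no abnormality rate.
- **The SAP has latitude.** Protocol 10 lets the SAP modify the outline and requires an amendment only for major changes to primary endpoints. It cannot be said that an amendment is required here. A deliberate change should still appear in SAP 2.1.
- **Protocol 8.2.1 guides care of individuals.** Recognising kidney injury at the time rests with the investigator and not on a final table. That is correct, but a long-term safety study also has to describe the pattern across participants.

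It is also true that no shift tables are planned for other panels. They are recommended here because change from baseline in a categorical result cannot be shown as a mean difference.

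**Conclusion.** The point holds as a gap in completeness and consistency. One of three safety laboratory panels, with 12 routine items, has no planned summary of measured values for a primary endpoint. The omission is undeclared, and the listed albumin-to-creatinine ratio endpoint has no analysis. Abnormalities reported as adverse events would still be seen. The study is descriptive and tests no hypothesis, so no error rate or power is affected. The effect on the safety conclusions cannot be sized, because the documents give no frequency of abnormal urine findings.

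The conclusion assumes that urinalysis was collected as scheduled and that no separate output plan covers it. The documents do not say whether urine protein and albumin are reported as categories or as numbers. That affects how they are summarised, not whether they should be.

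**What to change.** Add urinalysis to SAP 3.1.2, 6.1.2 and the Appendix 1 window tables.

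- **Categorical results (protein, albumin, blood, glucose):** shift from baseline to worst post-baseline category, with participants having both values as the denominator. If albumin or protein is numeric, use the descriptive statistics planned for chemistry.
- **pH and specific gravity:** descriptive statistics for observed values and change from baseline.
- **Windows:** the Week 12, Week 24 and every-12-weeks grid of SAP Table 4 (delayed start) and Table 5 (no delay) matches the urinalysis schedule. The averaging rule in their footnotes cannot be applied to categories. Where several categorical results fall in one window, use the worst.
- **Baseline:** state which value is used. SAP Appendix 1.2 takes the parent-study Week 12 value when the gap is under 7 days and otherwise sets baseline to missing, while Protocol Table 2 schedules urinalysis at the Baseline visit of this study. The choice decides who enters the shift tables.
- **If the omission is intended:** declare and justify it in SAP 2.1.
- **Albumin-to-creatinine ratio:** give it a derivation in 3.3 and an analysis in 6.3, or state that it is dropped.

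The cost is SAP wording and a few standard tables. The protocol already schedules urinalysis, so no new collection is needed for it.

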## 5. STUDY DESIGN

### 5.1. Overall Design

This multicenter, global, open-label extension study is designed to assess the safety of long-term treatment with osivelotor in participants with SCD. The study will be conducted globally and will be available to eligible participants enrolled in a prior Pfizer-sponsored osivelotor clinical study (originating study). Participants must meet the entry criteria for this

study to be eligible for enrollment (see Section 6.1). The study will have a global distribution, and up to approximately 500 participants will be enrolled.

Eligible participants will receive osivelotor administered orally daily if they continue to receive clinical benefit that outweighs risk, as determined by the Investigator, until the participant has access to osivelotor from an alternative source (eg, through commercialization or a managed-access program).

Eligible participants will receive open-label osivelotor at Baseline (Day 1). It is intended that Day 1 coincides with the final visit from the originating osivelotor study. End of Treatment (EOT) assessments from the originating study will serve as Baseline assessments for this study. If Day 1 for this study is greater than 7 days from the completion of the originating study, new baseline assessments will be obtained. If during the period between Day 1 of this study and completion of the originating study no dose is received for greater than 3 consecutive days, an appropriate loading dose will be administered prior to continued maintenance dosing (see Section 11.3 for detail). Additional assessments that may not have been included in the prior EOT assessments are outlined in the Schedule of Assessments and will need to be completed prior to study drug administration.

Participants who participated in Part A of C5351004 or any other open label osivelotor study, will undergo safety and outcome assessments at Baseline (Day 1) and every 12 weeks thereafter (Table 2).

Participants from Part B of C5351004, or any other randomized, blinded, placebo controlled osivelotor study will undergo safety and outcome assessments at Baseline (Day 1), Week 8, Week 16, Week 24, and every 12 weeks thereafter (Table 3).

Pediatric participants from Part C of C5351004 will undergo safety and outcome assessments at Baseline (Day 1), Week 2, Week 4, Week 8, Week 12, Week 16, Week 20, Week 24, and every 12 weeks thereafter (Table 4).

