### 11.5.2. Age-Specific Kidney Function Calculation Recommendations

At Screening, eGFR will be calculated using 2021 CKD-EPI eGFR equations (for adults 18 years and above), eCrCl will be calculated using Cockcroft-Gault formula (for adolescents 12 to <18 years), and eGFR will be calculated using Modified Schwartz Equation (for children 2 to <12 years), or Bedside Schwartz equation (for infants 6 months to <2 years).

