### 2.2.1. Primary Estimand(s)

The safety estimands for the primary endpoints will consider all safety data collected. Specifically, all data collected on or after obtaining informed consent will be included in the analysis.

**Population:** Patients with SCD as defined by the inclusion/exclusion criteria.

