**2.2.3. Study Design**

C5351005 (OLE) is designed as a multicenter, global, open-label extension study. The primary objective is to assess the long-term safety of osivelotor in participants with SCD. This study is available to eligible participants who have previously enrolled in a Pfizer-sponsored osivelotor clinical study and meet the entry criteria for this study.

Eligible participants will receive open-label osivelotor at Baseline (Day 1). It is intended that Day 1 coincides with the final visit from the originating osivelotor study. End of Treatment (EOT) assessments from the originating study will serve as Baseline assessments for this study. If Day 1 for this study is greater than 7 days from the completion of the originating study, new baseline assessments will be obtained. If during the period between Day 1 of this study and completion of the originating study no dose is received for greater than 3 consecutive days, an appropriate loading dose will be administered prior to continued maintenance dosing.

Only participants from C5351004 Part A (also referred to as the “parent study”) were enrolled into the OLE. C5351004 Part A is a study which enrolled only adult participants. There are two sets of participants rolling over from C5351004 Part A to the OLE study – (i) participants without a delayed start (Date of first dose in C5351005 – EOT date from C5351004 + 1 ≤ 42 days) and (ii) participants with a delayed start of OLE (Date of first dose in C5351005 – EOT date from C5351004 + 1 > 42 days). Each set follows a distinct schedule of assessments as outlined in the C5351005 protocol.

**3. ENDPOINTS AND BASELINE VARIABLES: DEFINITIONS AND CONVENTIONS****3.1. Primary Endpoint(s)****3.1.1. Incidence of TEAEs**

A treatment-emergent adverse event (TEAE) is defined as an AE that occurs during the effective duration of treatment defined as the time from the first dose of study drug through last dose of study drug + 56 days.

TEAEs that occur in the parent study are not counted as TEAEs in this study. In case, the start date of AE is the same date as the treatment start date and the question in the AE CRF page “Is this AE continuing from the parent study?” = “Yes”, then the event is not a TEAE,

as long as it can be confirmed that the AE in question had a start date in the parent study and no end date in the parent study.

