## **Appendix 1.2. Baseline Derivations**

### **Baseline derivation for labs, EPO, pharmacodynamic endpoints, weight and vital signs**

1. If the gap between EOT visit (EOT CRF form) from parent study and study day 1 from OLE study is  $< 7$  days (date of first dose of study drug in OLE – EOT visit date from parent study + 1  $< 7$ ), use Week 12 analysis visit assessment from the parent study to serve as the baseline. If this assessment is not available, baseline is set to missing.
2. If the above defined gap in #1 is  $\geq 7$  days, use the latest pre-dose day 1 assessment from OLE study to serve as the baseline.

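### SAP 3.1.2 drops all eGFR data of participants with a parent-study baseline, including extension values already in the right unit, and this is avoidable

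*SAP*

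**What the plan says.** Change in laboratory assessments is part of the primary endpoint. SAP 3.1.2 presents eGFR in mL/min/1.73m² and adds: "Data for participants whose baseline result (reported in mL/min) comes from the parent study will be excluded from the analyses".

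Appendix 1.2 of the SAP decides whose baseline that is. If first dose in the extension − parent EOT visit + 1 is below 7, the instruction is to "use Week 12 analysis visit assessment from the parent study to serve as the baseline". Otherwise it is to "use the latest pre-dose day 1 assessment from OLE study to serve as the baseline". Protocol 5.1 describes the short-gap route as the plan: "It is intended that Day 1 coincides with the final visit from the originating osivelotor study".

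For the primary estimand, SAP 2.2.1 says that "all data collected on or after obtaining informed consent will be included in the analysis". SAP 2.1, which lists departures from the protocol's analysis, does not mention the eGFR exclusion.

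**The concern.** The exclusion is worded by participant and covers the analyses without limit. It therefore removes more than a change score built on two units. It also removes eGFR values measured during the extension, which are in the unit the SAP wants. The people affected are those who moved straight from the parent study, and they are the most likely to have had uninterrupted exposure. Kidney function matters in this plan: Protocol 8.2.1 covers acute kidney injury, and Protocol 11.5 is a kidney-safety appendix that grades decline in eGFR.

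What is at stake is how completely one primary laboratory parameter is described. If the rule stands, the eGFR tables cover only participants who started at least 7 days after parent EOT by the SAP's count.

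**Working it through.** **Who is excluded.** Let D = date of first extension dose − parent EOT date.
- D + 1 < 7 means D = 0 to 5 days: parent baseline, eGFR excluded.
- D + 1 ≥ 7 and D + 1 ≤ 42 means D = 6 to 41 days: without delayed start, extension baseline, eGFR kept.
- D + 1 > 42 means D ≥ 42 days: delayed start, extension baseline, eGFR kept.

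The excluded set is therefore narrower than the SAP's group without delayed start.

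**Conflict with the estimand.** The estimand covers data from consent onward. A parent Week 12 value may predate consent to the extension, so not using it as a baseline is not in itself a contradiction. The contradiction lies in the post-baseline extension values, which are collected after consent and then dropped.

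**Size of the loss.** The documents do not give the share q of direct roll-overs, so q is an assumption. With equal variance in kept and excluded participants, the standard error of mean change rises by 1/√(1 − q):

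| q | Participants kept | SE ratio |
|---|---|---|
| 10% | 90% | 1/√0.90 = 1.05 |
| 25% | 75% | 1/√0.75 = 1.15 |
| 50% | 50% | 1/√0.50 = 1.41 |
| 90% | 10% | 1/√0.10 = 3.16 |

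**Why the two units cannot simply be mixed.** The parent-study formula is not in these documents, so two possibilities were tried. All participant values are assumed.
- Man, 30 years, creatinine 0.7 mg/dL, 85 kg, body surface area 2.05 m². CKD-EPI (Protocol 11.5.2.1): 142 × (0.7/0.9)^−0.302 × 0.9938^30 = 127.1 mL/min/1.73m². De-indexed: 127.1 × 2.05/1.73 = 150.6 mL/min, a false change of −23.5. Cockcroft-Gault: (140 − 30) × 85/(0.7 × 72) = 185.5 mL/min, a false change of −58.4.
- Woman, 30 years, creatinine 0.6 mg/dL, 50 kg, 1.5 m². CKD-EPI: 143 × (0.6/0.7)^−0.241 × 0.9938^30 = 123.2. De-indexed: 106.8, a false change of +16.4. Cockcroft-Gault: 0.85 × 110 × 50/(0.6 × 72) = 108.2, a false change of +14.9.

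Some action on the baseline is therefore justified.

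**Whether the loss is avoidable.**
- SAP 2.2.3 says only Part A participants enrolled and that "C5351004 Part A is a study which enrolled only adult participants". One equation is enough.
- Protocol 11.5.2 names 2021 CKD-EPI for adults. Its creatinine-only form needs creatinine, age and sex.
- Creatinine is in the chemistry panel (Protocol Table 9). Sex and date of birth are recorded (Protocol 9.1).
- Protocol Table 2 marks no chemistry at the extension Baseline visit for participants without delay. For direct roll-overs, the SAP's own change from baseline in creatinine already relies on the parent value.

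Using one equation at both times puts both values in mL/min/1.73m². With unchanged creatinine and age, the derived change is exactly 0, and neither weight nor body surface area is needed.

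**The case against.** The strongest reply is that little renal information is lost. Creatinine and blood urea nitrogen are chemistry tests summarized at baseline and each visit, with change, for everyone (SAP 3.1.2 and 6.1.2). Renal TEAEs are tabulated for the whole Safety Analysis Set. This stands. A reader might infer that kidney safety as a whole would be described only in participants with a treatment gap. The documents do not support that; only derived eGFR is affected.

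A reader might also infer that the retained group is biased. That is possible but not shown. The documented cause of delay is site activation (Protocol 6.1, inclusion criterion 1), which is administrative, and retained participants include some with a date difference of only 6 days.

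Nor do the documents show that most participants are lost. Delays were common enough for the SAP to define a delayed-start group, so the share could be low. The standard error is also not a planned statistic: SAP 5.3.2 reports n, mean, SD, median and range, and no hypothesis is tested. The ratios above indicate information lost and do not reproduce a planned result.

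Finally, the unit mismatch is the apparent reason for the rule, not a stated one. The sponsor may have meant to omit only change from baseline, but the sentence does not say so.

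**Conclusion.** The point holds in this form. As written, SAP 3.1.2 removes from the eGFR analyses every participant with D = 0 to 5 days, including their valid post-baseline extension values. This departs from the primary safety estimand and is not declared in SAP 2.1. The loss equals the unknown direct roll-over share; the 10% to 90% range is an assumption.

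The finding limits one primary laboratory parameter and leaves the other renal summaries intact, so it should be corrected but does not undermine the safety analysis. That the loss can be avoided rests on parent Week 12 creatinine being available to the analysis, which the documents support indirectly through Appendix 1.2 and Protocol Table 2.

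**What to change.** Replace the exclusion sentence in SAP 3.1.2 with:

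> Observed OLE eGFR values will be summarized by visit for all participants in the Safety Analysis Set. For change from baseline, eGFR at baseline and at each visit with scheduled eGFR will be derived from serum creatinine (mg/dL), age and sex using the 2021 CKD-EPI creatinine equation in Protocol 11.5.2.1, using the parent-study creatinine where Appendix 1.2 assigns a parent baseline. Participants without a baseline creatinine are omitted from change from baseline only. Values as collected will be listed.

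List the change in SAP 2.1. Limiting derivation to visits with scheduled eGFR avoids creating Week 12 values that Protocol Tables 1 and 2 do not plan. The missing-baseline clause keeps the text consistent with Appendix 1.2.

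One related cut-off needs reconciling. At D = 6 and 7 the SAP calls for an extension baseline, while Protocol 5.1 requires new baseline assessments only beyond 7 days, so some of these participants may have no baseline creatinine.

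The cost is SAP wording and one derived variable. Derived values may differ slightly from collected ones, which is why both should be available. If parent creatinine proves unavailable, the first sentence alone still restores the observed extension values.
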